14.8 Exploratory Endpoints

Exploratory endpoints will be described graphically and simple descriptive statistics will be provided for each variable at each time point.

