13. If a fresh biopsy of the primary or a metastatic lesion cannot be provided (e.g. inaccessible or patient safety concern) an archived specimen can be submitted only upon agreement from the study principal investigators. Refer to the SABRseq laboratory manual for further details on handling and shipping of tumour samples.
14. To be collected at screening, prior to SABR, prior to each pembrolizumab dose and 3 monthly during follow-up. Refer to the SABRseq laboratory manual for further details on blood sample collection, handling and shipping.

4. Background

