5.1 Hypothesis

This investigator driven Phase Ib study will examine the safety, efficacy and biological effects of two schedules of pembrolizumab, an antibody targeted against anti-programmed cell death 1 (PD-1), which will be given either before or after stereotactic ablative body radiotherapy (SABR) for metastatic NSCLC. We hypothesise that both arms i.e. 1) SABR followed by anti-PD-1 and; 2)anti-PD-1 with SABR after first cycle of pembrolizumab; will have clinically acceptable safety profiles with evidence of local and systemic efficacy; and that there will be differences in the immunological responses related to schedule of treatment.

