5.2 Objectives

Primary objective:

To assess common toxicities associated with pembrolizumab in combination with SABR when SABR is given before or after first cycle of pembrolizumab in patients with metastatic NSCLC.

Secondary objectives:

Secondary objectives are to examine the clinical efficacy of the combination:

- To describe response rate in: a) lesions treated with SABR, b) non-irradiated lesions and c) overall response, and compare between treatment arms
- To describe overall survival (OS) and progression free survival (PFS) and compare between treatment arms
- To describe the event history (progression at an irradiated lesion, progression at a non-irradiated lesion, appearance of a new lesion, ceasing treatment and death) of NSCLC patients treated with SABR in combination with pembrolizumab

Exploratory Objectives

- Evaluate PD-L1 expression in baseline tissue using immunohistochemistry.
- Evaluate baseline and longitudinal cellular and molecular changes in archival tumour tissue, and/or fresh tumour biopsies. This will include tumour infiltrating lymphocytes (TILs), CD73 and other markers.
- Evaluate longitudinal changes in immunological cellular subsets and cytokines within peripheral blood.

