Eligible patients will be randomised to either:

Arm 1: SABR followed by pembrolizumab; *or*

Arm 2: Pembrolizumab followed by SABR after cycle 1

Refer to Trial Schema

Pembrolizumab at a dose of 200 mg will be delivered every 3 weeks for a total duration of 102 weeks (34 cycles), commencing either 7 days (+/- 2 days) before the first dose of SABR or 7 days (+/-2 days) after the last dose of SABR.

Tumour response will be assessed according to RECIST 1.1, and irRECIST, Peter Mac Metabolic Response Criteria and PERCIST 1.0. Responses will be characterized in lesions treated with SABR and in un-irradiated lesions.

Peripheral blood samples and where possible, tumour tissue will be collected pre, during and post-treatment to assess baseline findings and longitudinal changes in immune subsets within tumour tissue and peripheral blood.

Evaluable patients are those that receive at least one dose of pembrolizumab and one dose of SABR. Non-evaluable patients will be replaced until the planned sample size has been reached.

7. Study Population

Patients with metastatic NSCLC who meet the inclusion/exclusion criteria described below will be eligible for participation in this study.

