8.2 Treatment Phase - ARM 1 (SABR followed by pembrolizumab)

8.2.1 SABR Visit Assessments

The following assessments must be performed prior to the first dose of SABR:

- Documentation of concomitant medications
- Blood samples for correlative studies

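### Section 14.8 plans no between-arm estimate for the immune hypothesis in 5.1, and tabulating blood markers by visit name would compare treated with untreated patients at two visits

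*Combined protocol and SAP*

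**What the plan says.** Section 5.1 ends its hypothesis with the statement "that there will be differences in the immunological responses related to schedule of treatment". It expects acceptable safety and efficacy in both arms, so this is the only difference between arms that it predicts.

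Section 5.2 states the blood objective as "Evaluate longitudinal changes in immunological cellular subsets and cytokines within peripheral blood". It attaches no arm comparison to it, although it does so for response and for survival ("To describe overall survival (OS) and progression free survival (PFS) and compare between treatment arms"). Section 5.3 words several exploratory endpoints as changes, for example in tumour-reactive T cells.

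Section 14.8 is the complete analysis: "Exploratory endpoints will be described graphically and simple descriptive statistics will be provided for each variable at each time point". By contrast, 14.5 tabulates toxicity by arm, 14.6 describes each arm and names a stratified log-rank test, and 14.7 names Fisher's exact test. Section 14.4 sets a two-sided 5% level for any arm test but assigns none to the markers.

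Footnote 14 to Tables 1 and 2 gives the blood sampling times: "To be collected at screening, prior to SABR, prior to each pembrolizumab dose and 3 monthly during follow-up". Section 6 sets the spacing of the two components, with pembrolizumab "commencing either 7 days (+/- 2 days) before the first dose of SABR or 7 days (+/-2 days) after the last dose of SABR".

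**The concern.** There are two separate gaps.

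1. **No estimate.** A prediction that the arms differ needs at least a stated between-arm quantity. Section 14.8 does not say that summaries will be shown by arm, and it does not say what change is measured from.
2. **An unspecified time axis.** The components come in opposite order, so a visit name does not mean the same exposure in the two arms. A table with rows labelled SABR and Cycle 1 would show arm differences that reflect only who has been treated so far.

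Section 4.13 expects the findings to serve as a basis for larger randomised studies. An arm difference produced by visit labels could be carried forward as a sequence effect. A real difference could also be left without an interval to judge it by.

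**Working it through.** **The plan's own figure.** The documents give no figure for the immune markers. The only sizing, in 14.9, is on toxicity, and it reproduces: 1 − 0.9^16 = 0.815 per arm and 1 − 0.9^32 = 0.966 overall. The smallest n giving at least 80% at a 10% rate is 16.

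**Exposure at same-named blood samples** (8.2.1, 8.2.2, 8.3.1, 8.3.2 and the 7-day spacing in Section 6). For Arm 1, 8.2.1 says "The following assessments must be performed prior to the first dose of SABR", which makes that sample pre-treatment.

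| Sample | Arm 1 | Arm 2 |
|---|---|---|
| SABR visit | untreated | about 7 days after pembrolizumab |
| Cycle 1 | about 7 days after SABR | untreated |
| Cycle 2 | both components given | both components given |

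**Time since SABR at Cycle 2.**
- Arm 1: SABR day 0, Cycle 1 day 7, Cycle 2 day 7 + 21 = 28. This is 28 days after SABR.
- Arm 2: Cycle 1 day 0, SABR day 7, Cycle 2 day 21. This is 21 − 7 = 14 days after SABR.
- With the ±2-day spacing window the ranges are 26–30 and 12–16 days. Adding the ±3-day dosing window in Section 10 gives 23–33 and 9–19 days. They do not overlap.
- Both arms are about 21 days after the first pembrolizumab dose.

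**Repeat biopsy.** Footnote 12 and 8.5 time it 3 months after SABR in both arms. There the arms match on SABR and differ by about 7 + 7 = 14 days in time since first pembrolizumab.

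**Does baseline adjustment cure the mismatch?** Simulation: 16 per arm, baseline correlation r = 0.5, 4,000 runs, no sequence effect. Either component shifts the marker by the same amount 7 days later. The shift and r are assumptions, because the documents give neither. Entries are the estimated difference and the rejection rate at 5%.

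| Shift | Cycle 1 by name, raw | Cycle 1 by name, ANCOVA | Aligned by exposure, ANCOVA |
|---|---|---|---|
| 0 | 0.00; 4.5% | 0.00; 4.4% | 0.00; 4.4% |
| 0.5 SD | 0.51; 28% | 0.51; 35% | 0.01; 5% |
| 1.0 SD | 1.00; 78% | 1.00; 88% | 0.00; 6% |

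Adjustment leaves the artefact whole and makes it easier to declare significant. Alignment removes it. The aligned result of zero depends on the two components having equal early effects. If they differ, the stage after the first component compares SABR alone with pembrolizumab alone. For that reason the main contrast belongs after both.

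**What baseline adjustment does give.** It multiplies the variance of an arm contrast by 1 − r², so the reduction is r²: 9% at r = 0.3, 25% at 0.5 and 64% at 0.8.

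**What 16 per arm can show.** Detectable difference at 80% power, two-sided 5%, normal approximation, in SD units: √(1 − r²) × (1.960 + 0.842) × √(2/16) = 0.99 × √(1 − r²).

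| r | Detectable difference | 95% CI half-width | Power for 0.5 SD |
|---|---|---|---|
| 0 | 0.99 | 0.72 | 29% |
| 0.3 | 0.94 | 0.69 | 32% |
| 0.5 | 0.86 | 0.63 | 37% |
| 0.7 | 0.71 | 0.52 | 51% |

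With 12 usable patients per arm (assumed), the detectable difference runs from 1.14 SD (r = 0) to 0.82 SD (r = 0.7).

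**The case against.** The best defence is that description is a legitimate choice for exploratory markers in a Phase Ib trial sized on toxicity. Section 5.2 adds an arm comparison where one is wanted and does not add it here. Section 14.8 speaks of time points and does not say that arms will be set side by side by visit name. Tables 1 and 2 list each arm's visits in that arm's own order. An exposure-aligned plot is fully compatible with the text, and 5.3 already frames several markers as change.

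Much of this stands. The visit artefact is a risk that the plan leaves open; it is not a comparison that the plan prescribes. The defence does not supply an estimate for a difference that 5.1 states as a hypothesis, nor a definition of baseline. Footnote 14 and 8.1 list a screening blood sample that the blood rows of Tables 1 and 2 do not mark, so the reference sample is open to choice.

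Four stronger readings are tempting, and the documents do not support them.

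- *The mismatch arises because baseline adjustment is missing.* It arises from the time axis, and adjustment leaves it in place.
- *All immune comparisons are affected.* Treated against untreated applies to two blood visits only, and not to the repeat biopsy.
- *Adjustment is worth a fixed gain in patients.* The equivalent size 16/(1 − r²) is 17.6 per arm at r = 0.3, 21.3 at 0.5 and 44.4 at 0.8. Each r is assumed, and the gain is measured against a raw contrast that the plan never makes.
- *The trial could settle the hypothesis if analysed properly.* At 16 per arm it could not do so reliably.

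**Conclusion.** The point holds as a free improvement to an exploratory analysis. No sample size or alpha figure in the documents is wrong on this account. The schedule-related immune hypothesis has no planned between-arm estimate, and that follows from the text alone. The treated-versus-untreated comparison is conditional: it appears if blood samples are tabulated by visit name, at the SABR and Cycle 1 visits. There it would carry the full early effect of whichever component came first, whatever size that is.

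The pre-Cycle 2 contrast keeps one limit that no analysis removes. Time since SABR, nominally 28 against 14 days, is determined by arm. It is part of the sequence contrast and cannot be separated from it.

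The precision figures rest on assumed correlations and on usable samples from all 16 patients per arm. With a detectable difference of about 0.7 to 1.0 SD for r from 0.7 to 0, the product is an exploratory estimate with an interval and not a test of 5.1.

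**What to change.** In 14.8, keeping the exploratory label:

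1. Define baseline as the last sample before any trial treatment: pre-SABR in Arm 1, pre-Cycle 1 in Arm 2.
2. Present blood markers by arm and by exposure stage (baseline, after the first component, after both), not by visit name.
3. Report the baseline-adjusted (ANCOVA) between-arm difference with 95% CI at the pre-Cycle 2 blood sample, and at the 3-month post-SABR biopsy for tissue markers. Use a log scale only where values allow, since zeros and values below detection would break a log ratio.
4. State that time since SABR at pre-Cycle 2 (nominally 28 against 14 days) is part of the sequence contrast. Repeat the contrast at later pre-dose samples, giving the number of patients contributing, because patients leave treatment and 14.4 plans no imputation.

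If the sponsor prefers description only, narrow the immune clause of 5.1 to match.

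The cost is a few lines of SAP text and a short program. No new blood samples or biopsies are needed: both arms already have a pre-treatment and a pre-Cycle 2 blood sample, and the repeat biopsy is already scheduled.

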14.9 Sample Size Calculation

This is a Phase Ib study with a sample size of 32 patients (16 in each arm). This study will assess the common toxicities associated with the combination of SABR and pembrolizumab. The sample size was determined such that, within each arm, the probability of observing toxicity in at least one patient was 80% for toxicities with true incidence rates of at least 10%. Table 9 illustrates different scenarios for true toxicity rates ranging from 5% to 30% with the respective probability of at least one patient presenting with the toxicity within the arm and overall.

Table 9: Probability of at least one patient presenting with a toxicity for different true toxicity rates

True toxicity rate	Within each arm (n=16)	Overall (n=32)
5%	0.560	0.806
10%	0.815	0.966
15%	0.926	0.994
20%	0.972	0.999

The table below shows the expected confidence interval for different response rate scenarios within each arm.

Table 10: Response rate and confidence intervals for different number of responses with n=16

Number of responses	Response rate (95% confidence interval)
6	37.5 (15 – 65)
8	50 (25 – 75)
10	62.5 (35 – 85)
12	75 (48 – 93)

Recruitment will occur over a two-year period. The principal analyses will be 24 months after the last patient has commenced treatment. An interim analysis assessing patterns of failure

and response to therapy based on post-therapy PET response will be performed once all recruited patients have completed 5 cycles of pembrolizumab therapy.

14.10 Early Termination Criteria

Consideration of suspension of patient accrual will occur if an unacceptable rate of toxicity is detected. The expected rates of grade 3+ pneumonitis and colitis are expected to be less than 5%. If at any given time during the trial 3 or more patients present with treatment related pneumonitis or colitis of grade 3-4 toxicity, data will be reviewed by the TMC and consideration will be given to permanently suspend recruitment and close the trial

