12.3 Serious Adverse Event Definition

Adverse events and adverse drug reactions are considered 'serious' if they threaten life or function.

Due to the significant information they provide, serious adverse events (SAE) (including Serious Adverse Drug Reactions) require expedited reporting. SAEs are defined as any adverse event or adverse drug reaction which:

- Results in death (i.e. fatal/grade 5 CTCAE)
- Is life-threatening (i.e. grade 4 CTCAE)
- Requires inpatient hospitalisation or prolongation of existing hospitalisation
- Results in persistent or significant disability/incapacity; or
- Is a congenital anomaly/birth defect
- Is a new cancer (that is not a condition of the study)
- Is associated with an overdose
- Other significant medical event*

*Medical and scientific judgment should be exercised in deciding whether expedited reporting is also appropriate in other situations, such as important medical events that may not be immediately life threatening or result in death or hospitalization but may jeopardize the patient or may require intervention to prevent one of the other outcomes listed in the definition above. These should usually be considered serious.

The following are NOT considered SAEs:

- Hospitalizations not intended to treat an acute illness or adverse event (e.g., social reasons such as pending placement in long-term care facility).
- Surgery or procedure planned before entry into the study. Note: Hospitalizations that were planned before the signing of the PICF, and where the underlying condition for which the hospitalization was planned has not worsened, will not be considered serious adverse events. Any adverse event that results in a prolongation of the originally planned hospitalization is to be reported as a new serious adverse event.
- Disease progression should NOT be reported as an adverse event or serious adverse event term; instead, signs and symptoms of clinical sequelae resulting from disease progression/lack of drug efficacy will be reported if they fulfill the serious adverse event definition.
- A standard procedure for protocol therapy administration will not be reported as a serious adverse event. Hospitalization or prolonged hospitalization for a

complication of therapy administration will be reported as a serious adverse event.

- The administration of blood or platelet transfusion. Hospitalization or prolonged hospitalization for a complication of such transfusion remains a reportable serious adverse event.

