12.8 Serious Adverse Event Reporting

12.8.1 Trial sites/investigators

All SAEs that occur from the time a patient has signed consent for the Trial to within 30 days of the final protocol-specified treatment are required to be reported to the Sponsor whether or not considered related to the treatment under investigation.

The Principal Investigator (PI) must:

- Determine whether an AE is 'Serious'
- For SAEs, the PI must then ascertain the suspected cause
- The attribution to the SAE must be recorded in the patients' medical records and reported on the SAE form.

SAEs must be reported by completing the SABRseq SAE form and emailing/faxing to the following:

Sponsor (or delegate)	[contact]
Merck Global Safety	[contact]
Merck Canada INC	[name] or [contact]

SAE forms are required at the following points:

Initial Report	Within one working day/24 hours of discovery or notification of the event. If the reporting of an SAE is delayed by more than 24 hours, an explanation must be provided on the SAE form.
Incomplete Reports	If all details are not available at the time of the initial report a completed report must be sent within the next 10 days.
Updated Report	If the event is not resolved (or 'on-going') at the time of the initial report, the SAE Form must be submitted every 30 days until the event is resolved, death has occurred or the condition has stabilised. If a change occurs in a stable condition (i.e. either worsens or improves), then a new SAE Form should be faxed

The Investigator is ultimately responsible for reporting the SAE and must sign the final SAE report(s). Should this Investigator not be available to sign the initial SAE form within the 24-hour period, a comment to this effect must be written on the form and the form signed by

the clinician attending to the patient at the time and faxed to the Sponsor. The investigator must sign the SAE form as soon as possible and re-fax to the Sponsor.

The Investigator at the Trial Site is responsible for determining the local SAE reporting requirements of the responsible HREC and subsequently notifying the HREC of SAEs as required.

All SAEs that have not resolved by the end of the study, or that have not resolved upon discontinuation of the patients participation in the study, must be followed until any of the following occurs:

- The event resolves
- The event stabilizes
- The event returns to baseline, if a baseline value/status is available

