17.3 Trial Management Committee (TMC)

The TMC will initially meet to assess safety after 3 patients in each arm has completed 8 cycles of pembrolizumab. Thereafter, the TMC will meet at 6 monthly intervals.

The TMC will comprise the following members:

- Radiation Oncology Principal Investigator
- Medical Oncology Principal Investigator
- An Independent Research Physician
- Clinical Trial Manager
- Trial Statistician

The C/PI will receive and review SAEs in real time.

The TMC will receive periodic safety reports therefore facilitating a response to potential safety issues. The TMC will also oversee study planning, monitoring, progress, review of information from related research, and implementation of recommendations from other study committees and external bodies (e.g. ethics committees). The primary mandate of the TMC would be to protect patient safety. If adverse events of a particularly serious type are more common than anticipated, the study can be considered for termination. Please see SABRseq TMC terms of reference for further information.

The TMC will consider whether to continue the study as planned, modify, or stop it, based on reports provided by BaCT or other information.

18. Publication and Presentation Policy

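### The only numeric safety trigger in 14.10 counts grade 3-4 pneumonitis or colitis, although the expected rate beside it is for grade 3+, so a case first recorded as fatal is not counted

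*Combined protocol and SAP*

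**What the plan says.** Section 14.10 (Early Termination Criteria) opens with a general provision: "Consideration of suspension of patient accrual will occur if an unacceptable rate of toxicity is detected". It then gives a benchmark, "The expected rates of grade 3+ pneumonitis and colitis are expected to be less than 5" (per cent). Its next sentence sets the only count in the section. If at any time "3 or more patients present with treatment related pneumonitis or colitis of grade 3-4 toxicity", the TMC reviews the data and considers closing recruitment and the trial.

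Section 12.3 separates the two top grades. One seriousness criterion is "Is life-threatening (i.e. grade 4 CTCAE" and another is "Results in death (i.e. fatal/grade 5 CTCAE".

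Three other provisions bear on a death:

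- Section 12.8.1 requires an initial SAE report "Within one working day/24 hours of discovery or notification of the event".
- Section 17.3 states: "The C/PI will receive and review SAEs in real time".
- Section 17.3 also states: "If adverse events of a particularly serious type are more common than anticipated, the study can be considered for termination".

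Section 14.5 tabulates patients with grade 3 or higher toxicity, so the safety analysis uses the open-ended range as well.

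**The concern.** Adjacent sentences of 14.10 use different grade ranges for the same two toxicities. The benchmark includes grade 5 and the count stops at grade 4. No section says that grade 5 adds to the count, and none gives a separate rule for a treatment-related death.

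Read literally, the worse outcome gives the lower count: a third patient with grade 3 pneumonitis triggers review, but a third patient whose pneumonitis is first recorded as fatal does not. This is the only trigger with a number, in a trial whose primary objective is toxicity.

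What is at stake is a missed or later formal TMC review, not an unseen death. Under 17.3 the first scheduled TMC safety meeting comes after 3 patients in each arm have completed 8 cycles (8 × 3 = 24 weeks of treatment for each of them), and later meetings are 6-monthly. The 14.10 count is the one numeric rule that brings data to the committee between meetings.

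**Working it through.** **Textual check (no assumptions).** Take two patients with treatment-related grade 3-4 pneumonitis and a third whose treatment-related pneumonitis is first recorded as fatal.

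- Count as written (grade 3-4): 2, trigger not met.
- Count on the benchmark's range (grade 3+): 3, trigger met.

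The case is limited to a patient first recorded at grade 5. Section 14.10 counts patients who present at grade 3-4 at any time, so a patient who passes through grade 3-4 and then dies can be read as counted. If the count were instead taken from the maximum grade per patient, as derived in 14.5, that patient could drop out too.

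**The plan's own figures.** The documents state no operating characteristic for this trigger. The nearest figures are in Table 9 (14.9), the probability of at least one case, 1 − (1 − p)^n. At 5% this gives 0.5599 (n = 16) and 0.8063 (n = 32), against 0.560 and 0.806 in the table. At 10% it gives 0.8147 and 0.9657, against 0.815 and 0.966. The 15% and 20% rows reproduce as well.

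**Illustrative size.** Inputs:

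- n = 32, both arms pooled, or n = 16 for one arm (14.9). Section 14.10 does not say which applies.
- p, the true per-patient rate of treatment-related grade 3+ pneumonitis or colitis. If the 5% ceiling covers both events together, p = 0.05. If it applies to each event and they are independent, p = 1 − 0.95² = 0.0975.
- f, the share of those cases fatal and never recorded at grade 3-4. This is an assumption. Section 4.12 reports 9 grade 3+ pneumonitis cases on pembrolizumab alone, 1 of them fatal, which suggests f = 1/9. If half of fatal cases are first counted at grade 3-4, f = 1/18.

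Formula: P(X ≥ 3), with X binomial(n, p) if grade 5 counts and binomial(n, p(1 − f)) as written.

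| n | p | As written, f = 1/9 | As written, f = 1/18 | Grade 5 counted |
|---|---|---|---|---|
| 32 | 1.8% | 0.014 | 0.017 | 0.020 |
| 32 | 3% | 0.053 | 0.061 | 0.070 |
| 32 | 5% | 0.169 | 0.191 | 0.214 |
| 32 | 9.75% | 0.533 | 0.575 | 0.616 |
| 32 | 10% | 0.550 | 0.593 | 0.633 |
| 32 | 15% | 0.819 | 0.851 | 0.878 |
| 16 | 5% | 0.032 | 0.037 | 0.043 |
| 16 | 9.75% | 0.156 | 0.178 | 0.200 |

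The 1.8% row is the pneumonitis rate in 4.12 (9/495), used here only as a low value for p.

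If exactly 3 patients have grade 3+ events, the written count falls short with probability 1 − (8/9)³ = 0.298, or 1 − (17/18)³ = 0.158 with f = 1/18.

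**How firm is f?** The exact 95% interval for 1 of 9 runs from 0.3% to 48%. At p = 5% and n = 32, the as-written probability runs over that interval from 0.213 to 0.049, against 0.214 if grade 5 counts. The gap could be almost nothing or most of the trigger's sensitivity.

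**The case against.** The best counter-argument concerns consequence. The trigger leads only to review and consideration, and the TMC can reach the same place for any grade through the general clause of 14.10 or its power in 17.3. Both can be read against the 5% benchmark, which does include grade 5: two grade 3-4 cases and one death are at least 3/32 = 9.4% of the planned sample. Deaths are reported within a day and reviewed as they arrive. Most fatal cases may have an earlier grade 3-4 record, and the single death in 4.12 says nothing on that. At rates below the ceiling the difference is small (0.014 against 0.020 at 1.8%). Other ambiguities in 14.10 matter more: pooled or per-arm counting moves the as-written figure at 5% from 0.169 to 0.032, and a combined or per-event reading of the ceiling moves it from 0.169 to 0.533. Section 17.3 also refers to separate TMC terms of reference, not available here, which may deal with deaths.

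All of this limits the size of the problem, and it stands to that extent. It does not remove the mismatch. The alternative provisions give no count, real-time review belongs to the coordinating or principal investigator and not to the committee, and a prespecified threshold should not depend on the reader supplying the grade that the text leaves out.

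**Conclusion.** The concern holds. Section 14.10 as written does not count a treatment-related pneumonitis or colitis case first recorded at grade 5, although its own benchmark covers that grade. It is probably a drafting slip, but it makes a stated decision rule give the wrong answer in a case that can be written down exactly.

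Confidence is high in the textual mismatch and low in any figure for its effect. With 32 patients pooled and f = 1/9, the shortfall is 0.214 − 0.169, about 4.5 percentage points at a 5% rate, and about 8 points at 9.75% to 10%. It roughly halves if half of fatal cases are counted first at grade 3-4. These figures rest on one death on pembrolizumab alone, from pneumonitis only, so they illustrate and do not estimate. The point should be fixed, because the trigger is the plan's only numeric safety rule and the repair is small.

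**What to change.** Reconcile the two sentences of 14.10 so that the count uses the grade range of its expected rate: treatment-related pneumonitis or colitis of grade 3 or higher, with grade 5 expressly included. Keep the threshold of 3, the counting of patients, and the consequence (TMC review and consideration) as they are. If the TMC terms of reference repeat the grade range, align them too.

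Do not define the count by reference to 14.5. That table covers only patients who received both pembrolizumab and SABR, and 14.3 collects no follow-up on the others, so a cross-reference could drop patients whom 14.10 now includes.

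The cost is one phrase, with no new data and no new committee. The trade-off is slightly more TMC reviews when toxicity sits at the expected ceiling. With f = 1/9 and 32 patients, the chance rises from 0.169 to 0.214 if the 5% is for both events together, or from 0.533 to 0.616 if it is for each event.
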